9.5 Dose Modification and Management of Toxicity

All subjects will begin treatment with tipifarnib at a starting dose of 600 mg bid in alternating weeks. If treatment-related, treatment-emergent AEs are observed meeting criteria for dose modification detailed further in this section, the dose level reductions summarized in Table 2 will be used.

Table 2: Tipifarnib dose levels

Dose Level	Alternate Week Schedule	
	Doses in mg (am + pm)	
Starting Dose	600 + 600	
-1	300 + 600*	
-2	300 + 300	

^{*}Depending on subject preference, the 600 mg dose may be taken in the morning or in the evening, as long as the total daily dose is 900 mg, i.e. 600 mg can be taken in the morning or evening with 300 mg taken for the other scheduled dose time. Tipifarnib should always be taken with a meal.

If treatment-related treatment-emerging CTCAE grade 4 non-hematological toxicity is observed, treatment with tipifarnib will be permanently discontinued.

If treatment-related treatment-emerging CTCAE \geq grade 3 hematological or grade 3 non-hematological toxicity is observed that cannot be managed with supportive care measures, treatment with tipifarnib will be interrupted until recovery to \leq grade 2. If recovery requires more than 4 weeks, treatment is to be discontinued. Upon recovery, tipifarnib may be restarted at the original dose or at the next lower dose level (see Table 2) at the discretion of the investigator. If grade 3 or 4 toxicity recurs, subsequent dose reductions may be conducted according to Table 2.

If treatment-related treatment-emerging CTCAE grade 2 renal toxicity is observed that cannot be managed with supportive care measures (including hydration and correction of electrolyte abnormalities, if appropriate), treatment with tipifarnib will be interrupted until recovery to \leq grade 1. Upon recovery to \leq grade 1, the subject may restart tipifarnib at their current dose level.

If treatment-related treatment-emerging CTCAE grade 2 renal toxicity recurs or if grade 3 renal toxicity is observed that cannot be managed with supportive care measures, treatment with tipifarnib will be interrupted until recovery to \leq grade 1. Additional treatment may be given at the next lower dose level (see Table 2) upon subject's recovery from toxicity. If grade 2 or 3 renal toxicity recurs, a subsequent dose reduction may be conducted. Reduced doses due to renal toxicity will not be re-escalated.

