Grade 2 Recurrent or Grade 3 Renal	Manage with BSC, including hydration and correction of electrolyte abnormalities, if appropriate. If not manageable, interrupt tipifarnib treatment until recovery to grade 1 or better	Upon recovery to ≤ grade 1, restart tipifarnib at the next lower dose level (see Table 2). If grade 2 or 3 renal toxicity recurs, upon recovery to ≤ grade 1, re-start tipifarnib at the next lower dose level (see Table 2).
Grade 2 non-tolerable Neurological	Manage with BSC. If not tolerable, interrupt tipifarnib treatment until recovery to grade 2 tolerable or better	Upon recovery to grade 2 tolerable or better, re-start tipifarnib at the next lower dose level (see Table 2).
		If grade 2 intolerable neurological toxicity recurs, upon recovery to grade 2 tolerable or better, re-start tipifarnib at the next lower dose level (see Table 2).
Grade 3 Neurological	Discontinue tipifarnib permanently	

In exceptional circumstances, dosing delays or skipping of dosing for reasons other than the management of toxicity will be allowed at the judgement of the investigator as long as 50% of the total dose is maintained in a given cycle.

Upon restarting tipifarnib following a treatment interruption, the cycle and dosing day are to be defined by the following:

- If a dose delay/interruption occurs and resolves within a cycle, dosing picks up where it left off
 - o For example, if a subject's treatment is held on Day 3, subject recovers 14 days later (nominal Day 17 in the cycle) and resumes tipifarnib treatment, the subject is considered to be dosing on Day 3 of the same cycle.
- If the delay goes beyond the cycle (> nominal day 28 of that cycle), upon recovery, the subject should be started at Day 1 of the next cycle.
 - o For example, if a subject's treatment is held on Day 3, subject recovers 30 days later (nominal Day 33 in the cycle) and resumes tipifarnib treatment, the subject is considered to be dosing on Day 1 of the next cycle.

Radiographic imaging for tumor response must maintain the fixed time schedule and is invariant to the drug exposure of the subject. Radiographic imaging will be performed at least once approximately every 8 weeks for 6 months, thereafter once approximately every 12 weeks. All other procedures/visits can follow the cycle's drug administration.

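### Protocol Section 9.5 gives conflicting instructions for some interruptions over 4 weeks: grade 3 renal toxicity meets two different rules, and the 30-day restart example names no toxicity

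*Protocol*

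**What the plan says.** All the relevant text is in Protocol Section 9.5, including Table 3.

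- **General rule.** It applies when treatment-related "grade 3 hematological or grade 3 non-hematological toxicity is observed that cannot be managed with supportive care measures" (for hematological events, grade 3 or higher). Tipifarnib is held until grade 2 or better. Then: "If recovery requires more than 4 weeks, treatment is to be discontinued". Table 3 repeats this sentence, only in the row for this class.
- **First grade 2 renal event.** If supportive care fails, hold until grade 1 or better; then "the subject may restart tipifarnib at their current dose level". No time limit is given.
- **Recurrent grade 2 or any grade 3 renal event.** If supportive care fails, hold until grade 1 or better; then "Additional treatment may be given at the next lower dose level (see Table 2) upon subject's recovery from toxicity". No time limit is given here or in the Table 3 row.
- **Grade 2 intolerable neurological event.** Hold until tolerable grade 2 or better, then the same restart wording. No time limit is given.
- **Permanent discontinuation.** Grade 4 non-hematological and grade 3 neurological events end treatment outright.
- **Delays for reasons other than toxicity.** Allowed in exceptional circumstances "as long as 50% of the total dose is maintained in a given cycle".
- **Numbering after a restart.** The lead-in is "Upon restarting tipifarnib following a treatment interruption, the cycle and dosing day are to be defined by the following". Under it, a delay running past nominal Day 28 leads to a start on Day 1 of the next cycle. The example is a subject held on Day 3; the "subject recovers 30 days later (nominal Day 33 in the cycle) and resumes tipifarnib treatment". It gives no toxicity, grade or reference to the 4-week limit.

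**The concern.** A prolonged toxicity hold forces a choice between restarting the drug and stopping it for good, so the protocol should give one answer for a given event. For grade 3 renal toxicity it gives two. The event is non-hematological and grade 3, so the general rule and its time limit apply on their face; it also has its own rule, with a different recovery grade and no limit. The example adds to the difficulty because it shows a restart after a hold longer than the stated limit and does not say which toxicities it covers.

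The stakes are first the safety of the individual subject. The choice also feeds planned outputs: treatment cycles, dose intensity and drug withdrawal (SAP Section 8.4), and adverse events leading to permanent discontinuation (SAP Section 10.1). The affected events are not remote. Creatinine elevation is named as a described effect of tipifarnib in the footnotes to Protocol Table 1. Section 9.4 lists hematological events, gastrointestinal disturbances and fatigue as the most common adverse events; at grade 3, when treatment-related and not manageable with supportive care, these fall in the class that carries the limit.

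**Working it through.** **1. Grade 3 renal toxicity under each reading.** Assume the event is treatment-related and supportive care has not controlled it. Let T2 be the days from the hold to grade 2 or better, and T1 the days to grade 1 or better, so T2 ≤ T1. The limit is 4 × 7 = 28 days.

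| Course | General rule | Renal rule as written | Renal rule with the 4-week limit carried over |
|---|---|---|---|
| T1 ≤ 28 | restart permitted at T2 | restart permitted at T1 | restart permitted at T1 |
| T2 ≤ 28 < T1 | restart permitted at T2 | restart permitted at T1 | discontinue |
| T2 > 28 | discontinue | restart permitted at T1 | discontinue |

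In the last row the two written rules require opposite actions. In the middle row the result depends on which recovery grade stops the clock and on whether the limit carries over. No sentence in the text or Table 3 settles either question. This result does not depend on the worked example.

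**2. Reproducing the numbering examples.** Nominal day = hold day + delay.

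- Companion example: 3 + 14 = 17, as stated.
- Example past the cycle: 3 + 30 = 33, as stated.

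**3. The 30-day example against the limit.** 30 − 28 = 2 days over, wherever the limit applies.

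**4. Does the numbering rule itself conflict with the limit?** For a Day 3 hold, the delay passes Day 28 once it reaches 29 − 3 = 26 days. Delays of 26 to 28 days (nominal Days 29 to 31) run beyond the cycle and stay within 4 weeks. The rule and the limit can therefore both hold; only the chosen 30 days exceeds the limit.

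**5. Which toxicities fit a 30-day recovery and restart?**

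| Event | Time limit | Restart after 30 days |
|---|---|---|
| Grade 3 or higher hematological | 4 weeks | contradicts the rule |
| Grade 3 non-hematological, other than renal and neurological | 4 weeks | contradicts the rule |
| Grade 3 renal | two rules | unresolved (step 1) |
| Grade 2 renal, first or recurrent | none stated | consistent |
| Grade 2 intolerable neurological | none stated | consistent |
| Grade 4 non-hematological; grade 3 neurological | permanent discontinuation | no restart arises |

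**6. Could the example be a delay unrelated to toxicity?** Planned dosing is Days 1–7 and 15–21, which is 14 days per cycle. A Day 3 hold leaves 2 dosing days (3 if Day 3 was dosed): 2/14 = 14%, 3/14 = 21%. Both are below 50%, so the general allowance for such delays does not cover it.

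**7. Weight of one decision.** On planned evaluable numbers, one subject handled differently moves a discontinuation percentage by 1/18 = 5.6 points in Cohort 1, 1/37 = 2.7 in Cohort 2 and 1/20 = 5.0 in Cohort 3. The documents do not say how many holds would exceed 28 days, so the total effect cannot be estimated.

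**The case against.** The strongest reply is that the example does not address eligibility to restart. Its lead-in presupposes a permitted restart and only assigns the cycle and day. The limit is stated twice in the same words, and a site would have to let a day-counting illustration override it. This largely stands. The example does not create an exception for grade 3 events, and different handling because of it would be a misreading. It does not stand completely: the bullet is phrased as an instruction on recovery, with no upper time limit and no toxicity restriction, so the misreading is foreseeable.

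A second reply is that the specific renal rule is meant to displace the general one. That may be the intent, but the protocol does not say so. Even if it did, whether the 4-week limit carries over would remain open.

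A third is that the example might describe recovery after salvage surgery, which Section 8.1 allows in responders. That is possible, and the documents do not say whether the 50% condition governs such an interruption. It is one more reason to label the example.

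A reader might also infer that Section 9.5 contradicts itself for every hold over 4 weeks, or for every grade 3 or higher event. The documents do not support that: the limit covers one class, several rules carry no limit, and some events end treatment regardless. Nor do they support an inference that ORR is compromised. Subjects who stop for reasons other than progression continue tumor assessments (Section 8.1), and the imaging schedule is independent of drug exposure (Section 9.5).

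**Conclusion.** The point holds in two parts of unequal weight. The main part is grade 3 renal toxicity: two rules apply, with different recovery grades and different time provisions, and when recovery to grade 2 takes more than 28 days they direct opposite actions. The secondary part is the unlabelled example, which exceeds the 4-week limit by 2 days for the one class that carries it and is consistent with the grade 2 renal, recurrent grade 2 renal and grade 2 intolerable neurological rules.

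Divergence between sites follows directly from the text for grade 3 renal toxicity and is only a foreseeable misreading for the example. The consequences are for patient safety, exposure and discontinuation counts. Their size is unknown because the frequency of such holds is not given, and no effect on ORR is shown. The conclusion assumes that grade 3 renal toxicity counts as grade 3 non-hematological toxicity, as the ordinary meaning of the words implies, and that the event is one that triggers a hold (Section 9.5 leaves asymptomatic laboratory findings to the investigator). The passages should be reconciled.

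**What to change.** Reconcile the passages in Section 9.5 and Table 3:

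- State which rule governs grade 3 renal toxicity, including which recovery grade ends the hold.
- State whether the 4-week limit reaches the renal and neurological rows.
- Either change the example past the cycle so that it lies inside the limit, or label the interruptions it covers and refer to the limit.

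The choice of clinical rule belongs to the sponsor; this point asks only for one consistent statement. The cost is a few lines in a protocol clarification or a memo to sites, with no added procedures or subjects.

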9.6 Treatment of Overdose

An overdose is defined as any dose greater than 20% over the daily tipifarnib dose. Any overdose must be recorded in the trial medication and adverse event sections of the eCRF. There is no known antidote for tipifarnib. In the event of overdose of tipifarnib, subjects should receive appropriate advice and supportive medical care by the Investigator or his/her designee and be followed-up accordingly.

For monitoring purposes, any case of overdose – whether or not associated with an AE (serious or non-serious) – must be reported to the Sponsor in an expedited manner.

9.7 Blinding

This is an open label study with no placebo or comparators.

9.8 Treatment Compliance

The importance of treatment compliance should be emphasized to the subject. Subjects will be given study drug and detailed instructions on how to take medications at home. Subjects will be instructed to return all used and unused study drug containers at each study visit. Subject compliance with the dosing schedule will be assessed by reconciliation of the used and unused

study drug at each clinic visit and review of the dosing diaries. The quantity dispensed, returned, used, lost, etc. must be recorded on the dispensing log provided.

Compliance will be monitored and documented by site personnel on the appropriate form. The site personnel will question the subject regarding adherence to the dosing schedule by reviewing the dosing diaries, recording the number of tablets (and strengths, if applicable) returned, the date returned, and determining treatment compliance (at least 80% of the total assigned dose) before dispensing new medication to the study subject.

9.9 Investigational Product Accountability

The Investigator or designee is responsible for maintaining accurate records (including dates and quantities) of IP received, subjects to whom IP is dispensed (subject by subject specific accounting), and IP lost or accidentally or deliberately destroyed.

9.10 Return and Disposition of Clinical Supplies

Unused tablets returned by the subject from a prior cycle of treatment may be re-dispensed to the subject. Study drug must be kept in a secure location for accountability and reconciliation by the Sponsor's designated clinical trial monitor. The Investigator or designee must provide an explanation for any destroyed or missing study drug or study materials.

Study drug may be destroyed on site, per the site's standard operating procedures, but only after the Sponsor or its designee has been notified and granted approval for drug destruction. All study drug destroyed on site must be documented.

Documentation must be provided to the Sponsor or its designee and retained in the Investigator's study files. If a site is unable to destroy study drug appropriately, the site can return unused study drug to the Sponsor or its designee upon request. The return of study drug or study drug materials must be accounted for on a form provided by the Sponsor or its designee.

All study drug and related materials should be stored, inventoried, reconciled, and destroyed or returned according to applicable state and federal regulations and study procedures.

9.11 Prior and Concomitant Medications

All prescription and over-the-counter medications taken by a subject within 28 days before the first study drug administration will be recorded in the eCRF. In particular, subjects will be asked about the use of agents that may affect the mevalonate pathway including statins (e.g. atorvastatin, simvastatin, rosuvastatin, pravastatin), bisphosphonates (e.g. pamidronate, risedronate, ibandronate, etidronate, alendronate) and nutritional agents (e.g. coenzyme Q_{10} , ubiquinone).

Supportive care medications considered necessary for the subject's safety and well-being may be given at the discretion of the Investigator. Any additional concomitant therapy that becomes

necessary during the trial and any change to concomitant drugs must be recorded in the corresponding section of the eCRF, noting the name, dose, duration and indication of each drug.

BSC will be provided by the clinical study sites according to local guidelines and standard practices.

[figure not shown]
Furthermore, the following treatments are allowed during the trial:

[figure not shown]
- Correction of electrolyte deficiency.
- Radiotherapy for pain control against non-target lesions as long as it does not influence bone marrow function.
- Total tumor resection in responding subjects who have become candidates for curative resection
- Hematopoietic growth factors and transfusions of blood or blood products in subjects
 who are experiencing hematological toxicity in accordance with standard institutional
 practice. However, such supportive care should not be used prior to hematological
 findings unless absolutely clinically necessary and after discussion with the Sponsor or
 designee's medical monitor.
- Antiemetic therapy in a subject experiencing gastrointestinal symptoms in accordance
 with standard clinical practice. If a subject experiences vomiting or nausea, prophylactic
 antiemetic medications may be administered with subsequent treatment in accordance
 with standard clinical practice.
- Concurrent use of bisphosphonates as well as Thyroid-Stimulating Hormone (TSH) suppressive therapy.

9.12 Non-permitted Treatments

Use of the following medications and therapies is not allowed during the trial:

- Investigational agents other than tipifarnib.
- Any other anticancer therapy, including radiation or surgery, for the primary disease
 under study with the exceptions of palliative treatment of non-target lesions and treatment
 of residual disease in study subjects who have experienced a partial response during the
 study.
- High dose systemic corticosteroids or any other immunosuppressive drugs except:
 - o Glucocorticosteroid treatment administered with a daily dose of \leq 20 mg prednisone or equivalent,
 - Single doses for the management of treatment-related AEs or for premedication of BSC agents.

- Sensitive substrates of CYP3A4 beginning Cycle 1 Day 1 and during the subject's participation in the tipifarnib treatment portion of this study.
 If continued concomitant therapy is needed, subjects should be transitioned to a medicine that is not a sensitive substrate of CYP3A4.
- Subjects should not use enzyme-inducing anti-convulsants (e.g. phenytoin, phenobarbital, and carbamazepine) while taking tipifarnib. If needed, subjects may use non-enzyme-inducing anti-convulsants (e.g. gabapentin, topiramate, valproate) while taking tipifarnib.

If the administration of a non-permitted concomitant drug becomes necessary during the trial, e.g., because of AEs or disease progression, the subject in question will be withdrawn from the trial, and the subject's data which will have been obtained before the withdrawal may be used for safety and efficacy evaluations.

